8.7 Immunogenicity

Blood samples for immunogenicity testing will be analyzed for the collected time points. Immunogenicity results will be analyzed descriptively by summarizing the number and percentage of subjects who develop detectable binding and/or neutralizing anti-imalumab antibodies.

Summaries will be based upon all subjects from the safety population. The effect of immunogenicity on PK, PD, efficacy and safety will be evaluated, but such analyses, if applicable, will be summarized in a separate report.

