10.3.1 Screening Assessments

After informed consent has been obtained, subjects will be screened on-site for eligibility based on the inclusion and exclusion criteria defined in [Section 9.1](#) and [Section 9.2](#), respectively. Screening procedures must be performed within 28 days prior to first imalumab administration (C1D1).

Screening assessments include the following:

- Eligibility evaluation (review of inclusion/exclusion criteria and completion of the required eligibility form)
- Demographics (date of birth, gender, race, and ethnicity)
- Relevant medical and surgical history
- Vital signs (body temperature, heart rate, blood pressure, respiratory rate, and weight)
- Physical examination
- ECOG PS
- 12-lead ECG
- ECHO/MUGA
- Clinical laboratory assessments (hematology, serum chemistry, and coagulation)
- Urinalysis
- Serum pregnancy test for women of childbearing potential
- Genetic testing (for KRAS and NRAS tumor status)
- CT or MRI scans for tumor measurement (as assessed by RECIST v1.1), unless results from CT or MRI scans performed within 28 days prior to first imalumab administration (C1D1), are available
- Blood sample for immunogenicity (anti-drug antibody [ADA] and neutralizing anti-drug antibody [NADA])
- Blood sample for PK assessment
- Blood sample for PD biomarkers (oxMIF and total MIF)
- Blood sample for cfDNA (genetic biomarkers)
- Urine sample for cfDNA (genetic biomarkers)
- Collection of AEs
- Review of concomitant medications/non-drug therapies
- Entry into IRT System

See the Schedule of Study Procedures and Assessments ([Table 3](#)) for additional details on screening assessments.

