10.3.3.8 End of Study/Early Termination Visit

Subjects who experience disease progression or who discontinue early from the study will be asked to undergo an End of Study/Early Termination visit. All questionnaires will be completed prior to the start of any assessments.

The following assessments will be performed at this visit:

- EORTC QLQ-C30
- EORTC QLQ-CR29
- EQ-5D
- Vital signs (body temperature, heart rate, blood pressure, respiratory rate, and weight)
- Physical examination
- ECOG PS
- 12-lead ECG
- Clinical laboratory assessments (hematology, serum chemistry, and coagulation)
- Urine dipstick test for women of childbearing potential
- Urinalysis
- CT or MRI scans for tumor measurement (as assessed by RECIST v1.1), if no disease progression was confirmed previously and this visit occurs > 4 weeks after the last scan; no additional scans will be required if disease progression is confirmed at this visit.

- For subjects treated with imalumab, blood sample for immunogenicity (ADA and NADA)
- For subjects treated with imalumab, blood sample for cfDNA (genetic biomarkers)
- For subjects treated with imalumab, urine sample for cfDNA (genetic biomarkers)
- Collection of AEs
- Review of concomitant medications/non-drug therapies
- Entry into IRT System

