13.4 Methods of Analysis

13.4.1 General Considerations

In general, descriptive summaries will be presented for the safety and immunogenicity variables collected. Continuous variables will be summarized using mean, standard deviation, minimum, median, and maximum. Categorical variables will be summarized using frequency counts and percentages. For time-to-event variables, Kaplan-Meier (KM) plots, median time-to-event, and other percentiles will be presented. For the purposes of

the data analysis, data cut-off for Part 2 will occur when 48 PFS events (progressions or deaths) have been observed.

Adverse events will be coded using the MedDRA and will be summarized by system organ class and preferred term. In addition, summaries of AEs by severity and relationship to study drug will be presented.

Further details are specified in the Statistical Analysis Plan.

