20.2 Schedule of Study Procedures and Assessments

Table 3
Schedule of Study Procedures and Assessments: Parts 1 and 2

Trial Periods	Screening Visit	Baseline Visit	Study Visits Per Treatment Cycle ^a				End of Study/ Early Termination Visit	Safety Follow-Up Visit ^b	
			Days 1 to 7	Days 8 to 14	Days 15 to 21	Days 22 to 28			
Study Days Procedures/Assessments	Days -28 to -1	Day 1 Predose							
Treatment Schedule									
Imalumab administration (QW) (Part 1; Part 2, Arm A)			Day 1	Day 8	Day 15	Day 22			
5-FU/LV or panitumumab administration (Q2W) (Part 1; Part 2, Arm A)			Day 1		Day 15				
Visit window (days)		± 2	± 2	± 2	± 2	± 2	± 2	± 7	
Informed consent ^c	X								
Eligibility criteria	X	X							
Demographics	X								
Relevant medical and surgical history	X								
Entry into IRT System	X	X ^d	Day 1 ^d	Day 8 ^d	Day 15 ^d	Day 22 ^d	X		
Vital signs ^e	X	X	Day 1	Day 8	Day 15	Day 22	X	X	
Physical examination	X	X	Day 1		Day 15		X	X	
ECOG PS	X	X	Day 1				X	X	

Table 3
Schedule of Study Procedures and Assessments: Parts 1 and 2

Trial Periods	Screening Visit	Baseline Visit	Study Visits Per Treatment Cycle^a				End of Study/ Early Termination Visit	Safety Follow-Up Visit^b
			Days 1 to 7	Days 8 to 14	Days 15 to 21	Days 22 to 28		
Study Days	Days -28 to -1	Day 1 Predose						
Treatment Schedule								
EORTC QLQ-C30		X					X	X
EORTC QLQ-CR29		X					X	X
EQ-5D		X					X	X
12-lead ECG ^f	X	X	Day 1				X	X
ECHO/MUGA	X							
Hematology ^g	X	X	Day 1	Day 8	Day 15	Day 22	X	X
Chemistry/coagulation ^g	X	X	Day 1	Day 8 (Cycle 1 only)	Day 15		X	X
Pregnancy test ^h (if applicable)	X	X	Day 1				X	X
Urinalysis	X	X	Day 1				X	X
Genetic testing ⁱ (KRAS/NRAS)	X							
Tumor measurement (RECIST v1.1) ^j	X					Day 28 of Cycle 2 and then every other cycle	X ^k	X ^k

Table 3
Schedule of Study Procedures and Assessments: Parts 1 and 2

Trial Periods	Screening Visit	Baseline Visit	Study Visits Per Treatment Cycle^a				End of Study/ Early Termination Visit	Safety Follow-Up Visit^b
			Days 1 to 7	Days 8 to 14	Days 15 to 21	Days 22 to 28		
Study Days	Days -28 to -1	Day 1 Predose						
Treatment Schedule								
Blood sampling for immunogenicity (ADA and NADA)	X						X	X
PK blood samples (imalumab plasma levels)	X	X	Day 1 and Day 2 OR Day 4 ^l	Day 8 ^l	Day 15 ^l	Day 22 ^l		
Blood samples for PD biomarkers (oxMIF and total MIF)	X	X	Day 1 and Day 2 OR Day 4 ^l	Day 8 ^l	Day 15 ^l	Day 22 ^l		
Blood sample for genetic biomarkers (cfDNA) ^m	X					Day 28 of Cycle 1 and then every other cycle	X	

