1. INTRODUCTION AND OBJECTIVES

The purpose of this study, in subjects with progressive measurable metastatic colorectal cancer (mCRC), is as follows:

- To evaluate the safety and tolerability of imalumab in combination with 5-fluorouracil (5-FU)/leucovorin (LV) or panitumumab to determine the recommended phase 2 dose (RP2D) of each combination
- To compare the efficacy of imalumab in combination with 5-FU/LV versus standard of care (SoC) (investigator choice) as third or fourth treatment line in subjects with KRAS mutated (mut) and/or NRAS mut tumors
- To compare the efficacy of imalumab in combination with panitumumab versus SoC (investigator choice) as third or fourth treatment line in subjects with KRAS wild type (wt) and NRAS wt tumors

Furthermore, the pharmacokinetic (PK) profile of imalumab in combination with 5-FU/LV or panitumumab will be characterized, and limited pharmacodynamic (PD) serum markers will be explored.

The statistical analysis plan outlines the methods for the planned final analysis in the protocol. As the study will continue to be on-going, an additional analysis addendum to the study report will be performed at the completion of the study.

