8.6 Vital Signs

For vital signs, the observed values and changes from baseline will be summarized by collected time points. Change from baseline will be calculated as (value at a treatment cycle – value at baseline). Frequencies and percentage of values meeting PCS criteria ([Table 5](#)) at any time post-baseline will be presented. The denominator for percentages will be the number of subjects who have a value at baseline and post-baseline.

Tables summarizing observed values and changes from baseline will be completed for the study cohorts. The number (%) of subjects with values that satisfy PCS criteria at any time during treatment will be provided for the study cohort and the integrated treatment group. PCS High criteria for BP are consistent with specific levels included in CTCAE criteria for Grade 1, 2, and 3 hypertension.

All vital sign data will be included in a by-subject data listing.

Table 5: Potentially Clinically Significant Post-Baseline Vital Signs

Vital Sign	Unit	PCS Low	PCS High
SBP	mmHg	Decrease from baseline \geq 30 Absolute value <80 mmHg	Increase from baseline \geq 30 Absolute value 121 – 139 Absolute value 140 – 159 Absolute value \geq 160
DBP	mmHg	Decrease from baseline \geq 20 mmHg Absolute value <60 mmHg	Increase from baseline \geq 20 Absolute value 80 – 89

Vital Sign	Unit	PCS Low	PCS High
			Absolute value 90 – 99 Absolute value \geq 100
Pulse	beats per minute	Absolute value \leq 40	Absolute value \geq 120
Respiratory Rate	breaths per minute	Absolute value < 12	Absolute value > 20
Weight	kg	\geq 7% decrease from Baseline	\geq 7% increase from Baseline

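### SAP 8.7 bases the anti-imalumab antibody percentage on the whole safety population, although some treated subjects will have no post-baseline sample at the 48-event cut-off, and this conflicts with protocol 13.3

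*SAP*

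**What the plan says.** Occurrence of binding and/or neutralizing anti-imalumab antibodies is a named secondary outcome (protocol 8.4.2.1; SAP 3.3). SAP 8.7 analyses it by "summarizing the number and percentage of subjects who develop detectable binding and/or neutralizing anti-imalumab antibodies" and adds: "Summaries will be based upon all subjects from the safety population". It gives no evaluability rule, no separate percentage denominator and no count of untested subjects.

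On sampling, protocol 10.3.1 places a baseline sample at Screening. The next entries are at the End of Study/Early Termination visit (10.3.3.8: "For subjects treated with imalumab, blood sample for immunogenicity (ADA and NADA") and the Safety Follow-up visit (10.3.3.9). Protocol Table 3 shows the same three time points and nothing during the treatment cycles. Tables 4 and 5, for standard of care, have no ADA row.

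On timing, protocol 13.4.1 says that "data cut-off for Part 2 will occur when 48 PFS events (progressions or deaths) have been observed". SAP section 1 says: "As the study will continue to be on-going, an additional analysis addendum to the study report will be performed", at study completion.

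On missing data, protocol 13.3 restricts everything except time-to-event endpoints to subjects who have data, and rules out imputation. SAP 5.5, which tabulates the departures from the protocol analysis, does not mention this rule.

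**The concern.** A subject can be shown to have developed antibodies only if a post-baseline sample exists. Under this schedule that sample comes after treatment ends. A subject still receiving imalumab at the 48th PFS event has only a screening result, and so does one who dies or is lost before the termination visit. If the percentage is taken over the full safety population, such a subject adds one to the denominator and cannot add to the numerator.

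The rate would then be too low by the untested fraction. The subjects missing because they are still on treatment also tend to have relatively long exposure to imalumab. Immunogenicity is a safety-relevant property of a monoclonal antibody, and a diluted percentage could be carried into later planning without anyone seeing how many subjects were never tested.

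**Working it through.** The plan states no ADA incidence, no ADA sample size and no missing-sample rate, so it has no figure of its own to reproduce. The check has two parts: what the passages say about the denominator, and how many subjects would be untested at cut-off.

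**Step 1. The passages side by side.**
- Protocol 13.3: available data only, no imputation. The denominator is the tested subjects.
- SAP 8.7: all subjects in the safety population. Read literally, the denominator is the tested plus the untested.
- SAP 8.6, the section just before, on vital signs: "The denominator for percentages will be the number of subjects who have a value at baseline and post-baseline". SAP 8.5 has the equivalent rule for ECG. SAP 8.7 has none.
- SAP 5.2, on missing data, covers AE causality, toxicity grade and assay limits. It neither repeats nor replaces the available-data rule.
- SAP 5.5 lists two changes from the protocol: the dropped interim analysis and the starting point for PFS. The ADA denominator is not among them.

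The two documents therefore give different denominators, and nothing resolves the difference.

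**Step 2. Untested subjects at cut-off.** Inputs from protocol 13.1: 44 subjects in Arm A and 22 in the control arm, median PFS 4.25 and 2.4 months, accrual over 12 months, drop-out 20% at 6 months, analysis at 48 events. Added assumptions: exponential PFS and drop-out, and uniform accrual. The monthly hazards are:
- Arm A: ln 2 / 4.25 = 0.163
- control: ln 2 / 2.4 = 0.289
- drop-out: −ln(0.80) / 6 = 0.037

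In 5,000 simulated trials I counted the Arm A subjects who had neither progressed nor dropped out at the 48th event. The mean was 7.4 of 44, the median 8, and the 10th to 90th percentile 4 to 11. These subjects have no scheduled post-baseline ADA sample by that date.

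**Step 3. Dilution if SAP 8.7 is read literally.** Let p be the positive rate among tested subjects, n = 44, and m the number untested. The reported rate is p × (n − m)/n, so the relative dilution is m/n.

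| m | m/n | Reported if p = 10% (assumed) | Reported if p = 20% (assumed) |
|---|---|---|---|
| 4 | 4/44 = 9.1% | 9.1% | 18.2% |
| 7.4 | 7.4/44 = 16.8% | 8.3% | 16.6% |
| 11 | 11/44 = 25.0% | 7.5% | 15.0% |

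The relative dilution does not depend on p. The two values of p only show the effect on an absolute scale.

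**Step 4. Dilution if protocol 13.3 is applied.** The denominator is n − m, the reported rate is p, and the dilution is zero.

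**The case against.** The strongest reply is that SAP 8.7 names an analysis population and does not define a denominator. SAP 8.5 supports this: it provides its ECG tables for the safety set, yet takes percentages over subjects with baseline and post-baseline values. Where the SAP does keep unassessed subjects in a denominator, as for response rate in 7.2.1.2, it says so and labels them not evaluable. On that view protocol 13.3 governs and nothing is diluted.

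Part of this stands. A reader might infer that the plan counts untested subjects as antibody-free and that immunogenicity will be understated. No passage says the first, and the second follows only if the SAP wording is applied literally. But the reply does not remove the conflict. The SAP does not carry 13.3 forward, its response-rate rule shows that 13.3 does not govern every percentage, and a programmer given the words of 8.7 could reasonably use the safety-set count.

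A reader might also infer that standard-of-care subjects dilute the rate further, because SAP 4.2 defines the safety set by study drug and SAP 5.3 suggests that this includes standard of care. The documents do not support this as a finding. SAP 5.4 and its Table 1 keep the standard-of-care cohorts separate, and 8.7 asks for no pooled column.

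Two further replies limit the size. Early termination is itself a sampling visit, and protocol 10.5 asks for every effort to have discontinued subjects attend it. The gap for ongoing subjects is also partly temporary, since they are due a sample when they stop and the SAP plans an addendum. Neither gives them a result at the 48-event analysis.

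**Conclusion.** The point holds as a conflict between SAP 8.7 and protocol 13.3 that SAP 5.5 does not declare. Followed literally, the SAP wording biases a named secondary outcome downward. It is not a demonstrated understatement, because the bias is absent if 13.3 is applied.

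Under the literal reading, the relative dilution in Part 2 Arm A is roughly 9% to 25% (about 17% at the mean of 7.4 untested). This rests on the protocol's planning assumptions, exponential times and uniform accrual. It treats subjects without progression or drop-out as still on treatment, and assumes the same antibody risk in tested and untested subjects. Deaths or losses before the termination visit would add to it, but the documents give no rate, so none is included. Part 1 subjects are outside the calculation.

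The summary is descriptive and the trial exploratory, so no test or decision rule is affected.

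**What to change.** In SAP 8.7, replace the sentence on the safety population with a rule along these lines:
- The denominator is imalumab-treated subjects with at least one post-baseline ADA result. For treatment-emergent ADA, restrict it further to subjects who were negative at baseline.
- Results are presented by study cohort and by integrated treatment group, as set out in SAP 5.4.
- The number of imalumab-treated subjects with no post-baseline sample is shown beside each percentage.
- The result is updated in the end-of-study addendum, once subjects who were ongoing at cut-off have been sampled.

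The count of untested subjects matters even with the right denominator. At cut-off the tested subjects are those who have already stopped treatment, and the reader needs to see how many longer-exposed subjects are not yet represented.

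The cost is a few lines of SAP text and one extra row in a table. The sampling schedule stays as it is, with no further blood draws or assays.

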9. EVALUATION OF PHARMACOKINETICS

A listing of PK blood sample collection times, derived sampling times, and imalumab concentrations will be provided.

Plasma concentrations of imalumab during Cycle 1 will be summarized by dose level, treatment group, and study day/measurement time interval using descriptive statistics (number of subjects [N], number of observations [n], mean, SD, coefficient of variation [CV%], median, minimum, and maximum). If n for a summary level is \geq 3, all descriptive statistics will be presented; if n = 2, mean, median, minimum, and maximum will be presented and all other descriptive statistics will be reported as not determined (ND); if n = 1, the single available value will be presented for mean, median, minimum, and maximum, and all other descriptive statistics will be reported as ND. For the 10 mg/kg treatment groups, concentrations will be summarized separately by study part and for

both study parts combined. Concentrations that are below the limit of quantitation (BLQ) will be treated as zero for the computation of descriptive statistics.

Subjects and/or data affected by protocol deviations or events that impact PK (such as incorrect dose, etc.) will be included in listings but excluded from descriptive statistics. A separate population PK analysis plan and corresponding report will be written to address the population PK analysis planned for this study.

10. EVALUATION OF QUALITY OF LIFE

10.1 Quality of Life Scoring

10.1.1 EORTC QLQ-C30 and QLQ-CR29

The European Organization for Research and Treatment of Cancer (EORTC) QLQ-C30 (version 3.0) ([Aaronson et. al., 1993](#)) supplemented by the colorectal cancer module (QLQ-CR29) ([Whistance et. al., 2009](#)) are validated instruments and will be used to measure quality of life and assess symptoms and side effects of treatment and their impact on everyday life.

The QLQ-C30 is composed of 5 multi-item functional scales (physical, role, social, emotional and cognitive functioning), a global health status/QoL scale, and 9 symptom scales (fatigue, nausea/vomiting, pain, financial impact, appetite loss, diarrhea, constipation, sleep disturbance and dyspnea).

The colorectal cancer module (QLQ-CR29) incorporates functional scales to assess body image, anxiety, weight, and sexual interest. The QLQ-CR29 also includes symptom scales to assess urinary frequency, blood and mucus in stool, stool frequency, urinary incontinence, dysuria, abdominal pain, buttock pain, bloating, dry mouth, hair loss, taste, flatulence, fecal incontinence, sore skin, embarrassment, stoma care problems, impotence, and dyspareunia.

Most items are answered on a 4-point scale (i.e., 1=Not at all, 2=A Little, 3=Quite a Bit, 4=Very Much) except the items contributing to the global health status/QoL, which have a 7-point scale (1=Very Poor to 7=Excellent). Raw scores (reported on eCRFs) will be transformed using a linear transformation to standardize the results so that scores for each functional and symptom scale range from 0 to 100.

The calculation for scoring these scales is the same in all cases ([Fayers et. al., 2001](#))

1. Calculate the average of the items that contribute to the scale; this is the raw score.

2. Use a linear transformation to standardize the raw score, so that scores range from 0 to 100; a higher score represents a higher ("better") level of functioning, or a higher ("worse") level of symptoms.

Calculations for raw score and linear transformation are as follows:

In practical terms, if items I_1, I_2, \dots, I_n are included in a scale, where n is number of items in the scale, the procedure is as follows:

Raw score

$$RS \text{ (Raw Score)} = (I_1 + I_2 + I_3 + \dots + I_n)/n$$

Linear transformation

Apply the linear transformation to 0-100 to obtain the score S ,

$$\text{Functional scales: } S = \{(RS - 1)/\text{range}\} \times 100$$

$$\text{Symptom scales / items: } S = \{(RS - 1)/\text{range}\} \times 100$$

$$\text{Global health status / QoL: } S = \{(RS - 1)/\text{range}\} \times 100$$

Range is the difference between the maximum possible value of RS and the minimum possible value.

The raw score and linear transformed score will be calculated when at least 50% of the items from the scale have been answered. Otherwise, the score will be missing.

The structure of this questionnaire and scoring are presented in [Table 6](#) and [Table 7](#).

Table 6: Scoring for QLQ-C30 version 3.0

Scale	Scale abbreviation	Number of items	Range	Item Number
Global health status / QoL				
Global health status/QoL	QL	2	6	29, 30
Functional scales				
Physical functioning	PF	5	3	1 to 5
Role functioning	RF	2	3	6, 7
Emotional functioning	EF	4	3	21 to 24
Cognitive functioning	CF	2	3	20, 25
Social functioning	SF	2	3	26, 27
Symptom scales / items				
Fatigue	FA	3	3	10, 12, 18

Nausea and vomiting	NV	2	3	14, 15
Pain	PA	2	3	9, 19
Dyspnoea	DY	1	3	8
Insomnia	SL	1	3	11
Appetite loss	AP	1	3	13
Constipation	CO	1	3	16
Diarrhea	DI	1	3	17
Financial difficulties	FI	1	3	28

Table 7: Scoring for QLQ-CR29

Scale	Scale abbreviation	Number of items	Range	Item Number
Functional scales				
Body Image	BI	3	3	15-17
Anxiety	ANX	1	3	13
Weight	WEI	1	3	14
Sexual interest (men)	SEXM	1	3	26 ^{a,c}
Sexual interest (women)	SEXW	1	3	28 ^{a,c}
Symptom scales / items				
Urinary frequency	UF	2	3	1,2
Blood and mucus in stool	BMS	2	3	8,9
Stool frequency	SF	2	3	22,23 ^b
Urinary incontinence	UI	1	3	3
Dysuria	DY	1	3	4
Abdominal pain	AP	1	3	5
Buttock pain	BP	1	3	6
Bloating	BF	1	3	7
Dry mouth	DM	1	3	10
Hair loss	HL	1	3	11
Taste	TA	1	3	12
Flatulence	FL	1	3	19 ^b
Fecal incontinence	FI	1	3	20 ^b
Sore skin	SS	1	3	21 ^b
Embarrassment	EMB	1	3	24 ^b
Stoma care problems	STO	1	3	25
Impotence	IMP	1	3	27 ^a
Dyspareunia	DSY	1	3	29 ^a

^a Note that items 26 and 27 are for men only, and items 28 and 29 are for women only. Thus, these questions will be answered only by a subset of patients.

^b When scoring scales or single items that include questions 19 to 24, use the answer to question 18: 'Do you have a soma bag (colostomy/ileostomy)? Yes/No to ensure that answers are taken from the relevant box of questions

^c In order for the two sexual interest scales to be interpreted as functional scales (i.e. a higher score is better), they should be scored according to the symptom scale algorithm.

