10.2 Analysis of QoL Data

For each QLQ-C30 and QLQ-CR29, the summary statistics of absolute scores and changes from baseline will be calculated for the linear transformed score for Global Health status, functional and symptom scale for the Safety Analysis Set.

For Part 2, the study drug and SoC is compared by a 2-sided Wilcoxon rank sum test with the t-Approximation at an alpha of 0.05.

For each of the 5 dimensions of the EQ-5D, tables will be provided to summarize the frequency and percentage of subjects with no, slight, moderate, and severe problems with or were unable to perform each dimension at baseline and end of study. In addition, the shift in the levels of perceived problems at baseline to the levels of perceived response at end of study will be summarized. The EQ VAS and change from baseline will be summarized by study cohort.

All summary tables will be provided for the study cohorts. Data for all subjects will be included in listings.

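### The SAP scores the EORTC functional scales with the symptom-scale formula, so eight functioning scores come out in the wrong direction

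*SAP*

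**What the plan says.** SAP Section 10.1.1 scores the QLQ-C30 and QLQ-CR29 in two steps. The items of a scale are averaged to a raw score RS, and RS is then rescaled linearly "so that scores range from 0 to 100; a higher score represents a higher" level of functioning, labelled as better, or level of symptoms, labelled as worse. The response key for all items except global health is "1=Not at all, 2=A Little, 3=Quite a Bit, 4=Very Much". Global health items run from 1 (very poor) to 7 (excellent).

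The printed line for functional scales, typesetting marks included, is "Functional scales: } S = \{(RS - 1)/\text{range}\} \times 100". In plain notation that is S = {(RS − 1)/range} × 100. The lines for symptom scales and for global health carry exactly the same expression. The text introducing the steps says the calculation does not differ between scales.

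Table 7 footnote c makes one exception. For the two sexual-interest scales to be read as functional scales, with higher meaning better, "they should be scored according to the symptom scale algorithm".

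Section 10.2 summarises the transformed scores and their changes from baseline, and adds a test between arms: "For Part 2, the study drug and SoC is compared by a 2-sided Wilcoxon rank sum test" at an alpha of 0.05.

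**The concern.** The section gives two scale types opposite meanings but the same arithmetic. With 4-point items, a formula that rises with RS gives high scores to subjects who answer at the very-much end. That suits symptoms. It suits functioning only if the functional items are worded positively, and footnote c implies that they are not.

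Comparing quality of life between arms is a secondary objective (protocol Section 7.3.4, SAP Section 1.1.2.4), and the QLQ-C30 is its instrument (SAP Section 3.5). If the formula is coded as printed, worsening functioning is tabulated as improvement and the favoured arm swaps on every affected scale. Global health is scored in the right direction, so the same table could show functioning and global health moving in opposite directions purely because of the scoring.

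**Working it through.** **Inputs, all from SAP Sections 10.1.1 and 10.2**
- Printed functional formula: S = {(RS − 1)/range} × 100.
- Range: 3 for every functional scale (Tables 6 and 7) and 6 for global health (Table 6).
- Item coding: 1 to 4, and 1 to 7 for global health.
- Stated direction: a higher functional score is better; a higher symptom score is worse.
- Footnote c: sexual interest uses the symptom algorithm so that higher is better.

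**Step 1: the stated 0-to-100 span.** With range 3, RS = 1 gives (0/3) × 100 = 0 and RS = 4 gives (3/3) × 100 = 100. For global health, RS = 7 gives (6/6) × 100 = 100. The span reproduces.

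**Step 2: the stated direction.** Compare the printed formula with its reflection, S′ = {1 − (RS − 1)/3} × 100.

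| RS | Printed S | Reflected S′ |
|---|---|---|
| 1 | 0 | 100 |
| 2 | 33.3 | 66.7 |
| 3 | 66.7 | 33.3 |
| 4 | 100 | 0 |

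S + S′ = 100 throughout, so one is the mirror image of the other.

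**Step 3: which one the SAP intends.** Footnote c names the symptom algorithm as the way to make sexual interest read as higher-is-better. If the functional algorithm also rose with RS, those two scales would already behave that way and the footnote would do nothing. It has content only if the ordinary functional algorithm falls as RS rises. Combined with the stated meaning of a high functional score, that makes a high RS on an ordinary functional scale the bad end. So the reflected formula is the one consistent with the rest of the section.

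**Step 4: effect on change from baseline.** The printed change is (RS₂ − RS₁)/3 × 100, and the reflected change is its negative. A worsening in mean item score from 1.6 to 2.2 gives (0.6/3) × 100 = +20 as printed, read as improvement, and −20 when reflected. A one-category worsening gives +33.3 instead of −33.3.

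**Step 5: effect on the arm comparison.** Reflection reverses all ranks, so a two-sided rank-sum p-value cannot change. As an illustration, five-item scales were simulated for 44 and 22 subjects, with item responses drawn evenly from 1–4 in the larger group and 1–3 in the smaller. These are not trial data.

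| | Printed | Reflected |
|---|---|---|
| Mean difference (larger − smaller group) | +19.24 | −19.24 |
| SD, larger group | 16.47 | 16.47 |
| Two-sided rank-sum p | 0.00007 | 0.00007 |

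Only the sign moves.

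**Step 6: scales affected.** Tables 6 and 7 list 5 + 5 = 10 functional scales. Sexual interest (men, women) is meant to use the symptom formula and comes out right, which leaves 10 − 2 = 8:
- QLQ-C30: physical, role, emotional, cognitive, social.
- QLQ-CR29: body image, anxiety, weight.

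Global health is not among the functional scales and is scored correctly, because its items already run upward to excellent.

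**The case against.** - **A leading term may have been lost in converting the PDF.** The argument turns on a missing 1 − in one typeset line, and footnote c would also fit a correct original. This cannot be excluded from extracted text alone. However, the line reads as complete, its braces balance, and it matches the two lines that follow it. It is worth one look at the source page, but it is not evidence against the point.
- **The item wording is not in the documents.** That the functional items ask about problems is inferred from the response key and footnote c, and the footnote does not show it scale by scale. That is true. But if the items were worded positively, the footnote would be pointless, so the section contradicts itself either way.
- **A programmer may score it correctly anyway.** The SAP states the direction in words, carries footnote c and cites a published scoring manual, so the slip might be noticed. The output would then depart from the approved formula without any record.
- **The reach is limited.** PFS, OS, response and safety are untouched. The three QLQ-CR29 scales are exploratory (SAP Section 3.6). SAP Section 5 treats secondary and exploratory p-values as descriptive, and reversed scores can be recovered as 100 − S. All of this stands and bears on how far the error spreads. It does not make a result with the wrong sign correct.

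**Conclusion.** The functional-scale formula is wrong as written. It contradicts the SAP's own definition of a high functional score and leaves footnote c without effect. Coded literally, it reverses eight of the ten scales listed as functional: all five on the QLQ-C30, which is the secondary quality-of-life measure, and three on the exploratory QLQ-CR29. Scores become 100 − S, and changes from baseline and arm differences change sign at full size. Spread and two-sided p-values do not move, so they would not reveal the error.

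The conclusion rests on the printed line being complete and on the item direction implied by footnote c. It should be corrected before the quality-of-life tables are produced. The primary analysis is not affected.

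**What to change.** Confirm the line against the source page, then make these changes in SAP Section 10.1.1:
- Functional scales: S = {1 − (RS − 1)/range} × 100.
- Symptom scales and global health: no change.
- Table 7 footnote c: keep it. With the corrected formula it becomes a real exception for items 26 and 28.
- Reword the introductory sentence saying the calculation is identical for all scales, so that it covers the averaging and rescaling but not the direction.

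A useful program check is that a subject with RS = 1 on physical functioning scores 100, and one with RS = 4 scores 0.

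The cost is one formula and one clause of text, plus one line of code. No data collection, sample size or test changes.
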